1.0 BACKGROUND, RATIONALE

Cardiac transplantation is currently the procedure of choice for selected patients with end-stage heart disease that is not amenable to further medical intervention or conventional cardiac procedures. Successful organ preservation is an important component of transplantation and ensures the maintenance of organ viability until implantation into the recipient. Currently, heart preservation for transplantation is limited to 4 to 6 hours of cold ischemic storage. Longer periods of ischemia are associated with poor outcomes post transplantation. In heart transplantation, preservation injury and ischemic reperfusion injury contribute to microvascular dysfunction and myocardial injury leading to primary graft dysfunction or to the activation of pro-inflammatory and pro-fibrotic processes, and the development of cardiac fibrosis and allograft vasculopathy.

In general, instructions for the use of organ preservation solutions state a temperature range of 2-8°C or 4-8°C, balancing the risk of cold injury at lower temperatures against the risk of hypoxic injury at higher temperatures. The standard method of storing donor hearts in preservation fluid within sequential bags that are then placed on ice and transported in a cooler does not allow for exact temperature control. The SherpaPak™ Cardiac Transport System has been developed to provide a safe, consistent method for cold ischemic storage of donor hearts for transplantation. Successful use of this device may decrease cold injury of donor hearts by maintaining the temperature consistently during transport and therefore may decrease primary graft dysfunction after transplantation.

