- Two (2) episodes of severe primary graft dysfunction (PGD) per ISHLT grading criteria (left or right ventricle, not including rejection or cardiac tamponade) requiring use of a mechanical circulatory support (MCS) device within 24 hours after transplant in subjects randomized to the SherpaPak method of transport.
- Two (2) deaths occur in subjects randomized to the SherpaPak method of transport within 7 days after transplant.

It is the responsibility of the Principal Investigator to report all of the above SAEs to the DSMB within 24 hours of discovering the event.

In the event that the study is suspended, no new subjects will be consented or randomized to the trial. Subjects already in follow-up on the study will continue to be followed as outlined in the protocol unless the appointed Chair provides further recommendations.

All heart graft-related adverse events and serious adverse events are to be recorded on the electronic case report forms until post-transplant day 30. The description of the adverse event will include: the date of onset, duration, severity, seriousness, the relationship of the event to the trial treatment, anticipated or not, and any treatment required. All serious adverse events occurring during the course of the first 30 days post-transplant will be documented on the appropriate electronic case report form(s) in REDCap. Heart graft-related AEs will be recorded up to the 30-day follow-up or through hospital discharge if longer than 30 days. The principal investigator is responsible for the classification and reporting of heart graft-related adverse events to the appropriate regulatory authorities.

A SAE is any AE that in the view of the Investigator results in death, is life-threatening, requires inpatient hospitalization or causes prolongation of existing hospitalization. In the interest of patient safety, and in order to fulfill regulatory requirements, all SAEs (regardless of their relationship to the study procedures) will be documented and reported per IRB guidelines. In the interest of this study, the SAEs that meet the stopping rule criteria within the DSMB Charter, will be submitted to the DSMB for review.

Heart-graft related-AEs will be captured in this study. The investigator will assess the relationship of the AE to the SherpaPak Cardiac Transport System or to the standard of care methods of preservation. The relationship will be assessed using the following categories:

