- Definitely Related: There is a reasonable causal and temporal relationship between preservation with the SherpaPak Cardiac Transport System and the adverse event.
- Probably Related: It is more likely than not that there is a reasonable causal relationship between preservation with the SherpaPak Cardiac Transport System and the adverse event.
- Possibly Related: There is a reasonable relationship with preservation with the SherpaPak Cardiac Transport System and the adverse event, but the causal relationship is unclear or lacking.
- Unlikely Related: There is a temporal relationship with preservation with the SherpaPak Cardiac Transport System and the adverse event, but there is not a reasonable causal relationship between the trial device and the event.
- Unrelated: There is no relationship between preservation with the SherpaPak Cardiac Transport System and the adverse event.

The investigator will rate the severity of the adverse event using the following categories:

- Mild: The adverse event is transient and/or easily tolerated by the subject.
- Moderate: The adverse event causes the subject discomfort and interrupts the subject's usual activities.
- Severe: The adverse event causes considerable interference with the subject's usual activities.

During the trial, investigators will be responsible for complete and accurate entry of data into the trial's REDCap database, and will maintain on file the following accurate, complete and current records relating to this trial:

- All relevant correspondences and required reports that pertain to the trial
- Records of receipt, use or disposition of the investigational device, including the type and quantity of the device; the dates of receipt; the lot number; the names of all persons who received, used or disposed of each device; and why and how any units of the device have been returned to the Sponsor, repaired, or otherwise disposed
- Records of each subject's case history and exposure to the device
- Signed and dated consent forms
- Protocol, and any amendments
- Investigator curriculum vitae

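### The five causality categories for adverse events name only SherpaPak, so a control-arm event can literally be rated only Unrelated

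*Combined protocol and SAP*

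**What the plan says.** Section 6.1 (Data and Safety Monitoring Plan) states the task for both arms: "The investigator will assess the relationship of the AE to the SherpaPak Cardiac Transport System or to the standard of care methods of preservation". It then ties that task to a single scale: "The relationship will be assessed using the following categories".

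The scale has five levels. The top one is "Definitely Related: There is a reasonable causal and temporal relationship between preservation with the SherpaPak Cardiac Transport System and the adverse event" and the bottom one is "Unrelated: There is no relationship between preservation with the SherpaPak Cardiac Transport System and the adverse event". The three in between (Probably, Possibly and Unlikely Related) also refer to preservation with SherpaPak. Unlikely Related adds a second reference to the device: "there is not a reasonable causal relationship between the trial device and the event". No separate scale or instruction for control-arm events appears anywhere in the document.

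Earlier in the same section, the items to be recorded for each event include "the relationship of the event to the trial treatment", which does not name either method.

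**The concern.** The protocol asks a question about two preservation methods and gives answers for one. For a heart kept in standard cold storage, an investigator who follows the definitions must choose Unrelated whatever the suspected cause. An investigator who follows the lead-in sentence must apply a definition that is not written down. Different raters may resolve this differently.

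The gap falls on the harm the trial was set up to study. Section 1.0 says of standard storage that hearts "placed on ice and transported in a cooler does not allow for exact temperature control", and of SherpaPak, "Successful use of this device may decrease cold injury of donor hearts by maintaining the temperature consistently during transport". Cold injury after standard storage is the suspected mechanism, yet an event attributed to it has no usable category except Unrelated. If relatedness were listed by arm, preservation-related events could appear only under SherpaPak. That would be a product of the wording, and it would count against the device.

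**Working it through.** The plan gives no figure to reproduce, and the point depends on no rate, power or variance. The check is a comparison of text and a count.

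**Definitions by the method they name (Section 6.1)**

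| Category | What it requires | Method named | Can be literally true for a control heart? |
|---|---|---|---|
| Definitely Related | causal and temporal link | SherpaPak | No |
| Probably Related | causal link more likely than not | SherpaPak | No |
| Possibly Related | reasonable link, causation unclear or lacking | SherpaPak | No |
| Unlikely Related | temporal link only | SherpaPak, and again as the trial device | No |
| Unrelated | no link | SherpaPak | Yes |

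The first four each need some relationship with an exposure that a control heart did not have. Hence:

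- definitions naming SherpaPak: 5 of 5;
- definitions naming standard storage: 0 of 5;
- categories open to a control recipient: 1 of 5, against 5 of 5 for a SherpaPak recipient.

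**How many subjects could be affected.** Section 3.4 gives 1:1 randomization and Section 4.0 gives approximately 20 subjects, so the expected control arm is 20 × 0.5 = 10. Section 4.0 ends that sentence with *respectively*, which could mean 20 per arm; the total would then be 40, and 40 × 0.5 = 20. Only control subjects with a recorded event are affected. The documents give no event rate, so the range is 0 to about 10 (or about 20). These upper figures are expected arm sizes and not strict limits, and they count subjects although ratings are made per event.

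**What uses the rating**

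- The main safety measure in Section 6.1 is defined by a list of event types: not affected.
- The suspension criteria count severe graft dysfunction with mechanical support, and deaths, in SherpaPak subjects: not affected.
- Serious events are documented and reported whatever their relationship: not affected.
- Sections 7.1 and 7.2 plan generic descriptive summaries and do not name relatedness: no specified analysis is affected.

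**Size of the correction.** The SherpaPak preservation phrase occurs once in each of the five definitions and the trial device once: 5 + 1 = 6 replacements.

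**The case against.** The strongest reply is that the intent is plain. The lead-in sentence names both methods, so a sensible investigator would read the assigned method into each definition, and rating a control event Unrelated while blaming cold storage would not do what that sentence asks. No planned output uses the rating, so the one-sided table is hypothetical. Ratings are entered on a REDCap form that is not in the documents and may already be worded for both arms.

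All of this is fair, and it is why the point is minor. It does not make the definitions right. Clear intent in the lead-in is what shows the list to be wrong, and relationship is a required item for every recorded event.

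Two smaller points also deserve an answer. The term used for the recorded item, trial treatment, is not defined; it reads naturally as either arm, but that is an inference. The conflict could also be removed by limiting the scale to SherpaPak and cutting the lead-in sentence back. That would be consistent, but it would drop the two-arm assessment that the protocol expressly asks for.

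**Conclusion.** The concern holds as a minor error of wording. The lead-in and the list in Section 6.1 cannot both be followed for a control-arm event: one of the five categories is literally available to a control recipient, and it is the one that denies any relationship. The damage is confined to the comparability of causality ratings between arms, in at most the control subjects who have a recorded event.

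Confidence in the mismatch is high, because it rests only on the text. Whether any rating has actually been distorted cannot be told from the documents; that depends on the REDCap form and on how investigators have read the list.

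**What to change.** In all five definitions, replace the reference to preservation with SherpaPak by *the assigned preservation method (SherpaPak or standard cold storage)*. In Unlikely Related, replace the reference to the trial device in the same way. The item on relationship to the trial treatment can stay; a short note that it means the assigned method would remove any doubt.

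Check that the causality field on the REDCap adverse event form matches the new wording, and review any control-arm ratings already entered. SherpaPak-arm ratings do not change in substance.

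The cost is a small wording amendment with six replacements in one list, a check of one form field, and a brief review of existing control-arm entries.

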6.2 QUALITY CONTROL AND QUALITY ASSURANCE

- The investigator is required to keep accurate records to ensure that the conduct of the study is fully documented. An internal auditor will regularly review the conduct of the trial, verify adherence to the protocol, and confirm the completeness, consistency, and accuracy of all documented data.

7.0 STATISTICAL CONSIDERATIONS

7.1 STUDY OUTCOME MEASURES

Continuous variables will be summarized using descriptive statistics, specifically the mean, median, standard deviation, minimum, and maximum. Categorical variables will be summarized using frequencies and percentages.

7.2 SAMPLE SIZE CONSIDERATIONS

The study is intended to serve as a proof of concept study. Comparative analyses will be primarily descriptive due to a small sample size.

